16.3.1 Overview of changes

Amendment 5 is the third global amendment dated 15 Nov 2016.

16.3.1.1 Change 1: Change Medical Expert's name

The surname of the sponsor's Medical Expert we updated.

Rational:

The surname of the sponsor's Medical Expert changed during the course of the study and was adjusted accordingly.

Affected sections: [Title page](#)

16.3.1.2 Change 2: Change of sponsorship information

The sponsor was changed from Bayer Healthcare AG to Bayer AG for non-US territory and sponsor information for Bayer Healthcare Pharmaceuticals Inc. was added for US-territory.

Rational:

Bayer HealthCare AG merged with Bayer AG, an affiliated company within the Bayer Group, effective as of 1st July 2016. Thereby, Bayer HealthCare AG ceased to exist and Bayer AG became its legal successor and automatically took over all of the Bayer HealthCare AG's

rights, obligations and liabilities by law. As a result of the above mentioned merger, Bayer AG assumes the role of the sponsor.

Affected sections: [Title page](#)

16.3.1.3 Change 3: Modification of dosing regimen

The total daily dose will be increased by 50% for all body weight groups. This will be achieved by three times daily administration of the same individual dose previously used with the b.i.d. schedule.

Rationale:

Rivaroxaban was well tolerated in the 5 children treated according to the b.i.d. regimen and there were no bleeding events. Furthermore, no symptomatic recurrent venous thromboembolic complications occurred. Repeat imaging of the thrombosis in two children with a persistent thrombosis at the start of rivaroxaban treatment showed normalization and substantial regression of the thrombosis, respectively, after the 7-day treatment with rivaroxaban.

However, PK results of the first 5 children enrolled with the b.i.d. regimen indicate lower rivaroxaban exposure ($AUC_{ss,24h}$) and C_{trough} concentrations than initially expected by the PK model.

Based on these observations the Data Monitoring Committee in its meeting on September 19, 2016, identified an efficacy concern. The DMC clarified that “the efficacy concern the committee identified was related to the potential for the low levels to be associated with thrombotic events, not related to any observed events in the patients treated to date.” The DMC recommended to change the dosing regimen from a b.i.d. (approx. 12-hour intervals) to a t.i.d. (approx. 8-hour intervals) schedule, applying the same individual doses previously administered twice daily. This recommendation was endorsed by the steering committee.

The 50% increase of the total daily dose aims to elevate the exposure to the lower end of the adult reference range. The shortening of the dosing interval from 12 hours (b.i.d. schedule) to 8 hours (t.i.d. schedule) aims to increase the C_{trough} concentrations to match the adult reference range which will allow to extrapolate safety and efficacy from the adult VTE treatment population.

The change from b.i.d. to t.i.d. schedule requires an adaptation of PK/PD sampling timepoints and instructions for administration of rivaroxaban.

The original protocol included dosing information for children with body weight of 12 to < 20 kg. This specific dosing information was deleted as this body weight group does not apply to children aged younger than 6 months.

Affected sections: [Synopsis](#), [Section 1 Introduction](#), [Section 3.1 Study description](#), [Section 5.1.1 Rivaroxaban regimen](#), [Section 6.3 Visit 2 – Treatment visit at Day 1](#), [Section 6.4 Visit 3 – Treatment visit at Day 3](#), [Section 6.5 Visit 4 – Day 8](#), [Section 6.12 PK/PD assessment](#)

16.3.1.4 Change 4: Provision of additional imaging tests for adjudication

Investigators are asked to also submit diagnostic tests other than ultrasound for evaluation of repeat imaging by the Central Independent Adjudication Committee, if available.

Rationale:

Repeat imaging will provide valuable efficacy information. The protocol requires repeat ultrasound imaging before start and after completion of the 7-day rivaroxaban treatment. If other imaging tests (e.g., CT, MRI) are planned and conducted independently of the study protocol, these imaging tests may support the evaluation of the status of the thrombosis and should therefore be submitted for adjudication, in addition to the ultrasound imaging required by the protocol.

Affected sections: [Section 6.3 Visit 2 – Treatment visit at Day 1](#); [Section 6.5 Visit 4 – Day 8](#)

16.3.2 Changes to the protocol text

In this section, all affected protocol sections are detailed; the sequence of the sections follows the structure of the original protocol. In the display of modifications, the “old text” refers to the protocol version preceding this amendment. Deletions are ~~crossed-out~~ in the “old text”. Additions are underlined in the “new text”. Corrections of typing errors or omissions are not highlighted in this amendment.

16.3.2.2 Synopsis

This section was modified based on Change 3.

Old text:

[...]

Dose(s)

Age- and body weight-adjusted ~~twice~~ daily dosing of rivaroxaban to achieve a similar exposure as that observed in adults treated for venous thromboembolism (VTE) with 20 mg rivaroxaban once daily

[...]

Methodology

Children with confirmed arterial or venous thrombosis who have been treated with anticoagulant therapy for at least five days. Children will receive an age- and body weight-adjusted rivaroxaban regimen using an oral suspension (1 mg/mL) for a total of 7 days followed by an observational period of another 30 days. Rivaroxaban will be administered ~~twice~~ daily. An ultrasound will be performed at day 1 and 8 of rivaroxaban treatment to document asymptomatic changes. In addition, children will be monitored for the occurrence of symptomatic recurrent thrombosis and bleedings. All suspected clinical study outcomes and baseline and repeat ultrasound imaging tests will be assessed by a Central Independent Adjudication Committee (CIAC).

An independent data monitoring committee (DMC) will monitor the children's safety and give recommendations to the steering committee.

[...]

Table 2: Flow chart: pharmacokinetics and pharmacodynamics

Pharmacokinetics and pharmacodynamics (PK/PD) ^a	Visit 1	Visit 2				Visit 3				Visit 4
Rivaroxaban treatment days	Screen day -10 to day 1	Treatment day 1		Treatment day 2		Treatment day 3		Treatment day 4 to 7		Day 8
Rivaroxaban administration		1 st dose	2 nd dose	1 st dose	2 nd dose	1 st dose	2 nd dose	1 st dose	2 nd dose	
PK/PD time points		0.5 to 4.5 hr post dose	2-4 hr post dose			2-8 hr post dose				10-16 hr after last dose at day 7
Obtain blood sample for PK ^b		•	•			•				•
Obtain blood sample for PD ^c			•			•				•

hr = hour(s), PD = pharmacodynamics, PK = pharmacokinetics

^a The approximate total blood volume taken per child for PK/PD is 6.6 mL. Always draw the PD sample as the last sample.

^b Blood volume per PK sample is approximately 0.6 mL; total blood volume for all PK samples is 2.4 mL.

^c Blood volume per PD sample is approximately 1.4 mL; total blood volume for all PD samples is 4.2 mL.

New text:

[...]

Dose(s)

Age- and body weight-adjusted three times daily dosing of rivaroxaban to achieve a similar exposure as that observed in adults treated for venous thromboembolism (VTE) with 20 mg rivaroxaban once daily

[...]

Methodology

Children with confirmed arterial or venous thrombosis who have been treated with anticoagulant therapy for at least five days. Children will receive an age- and body weight-adjusted rivaroxaban regimen using an oral suspension (1 mg/mL) for a total of 7 days followed by an observational period of another 30 days. Rivaroxaban will be administered three times daily. An ultrasound will be performed at day 1 and 8 of rivaroxaban treatment to document asymptomatic changes. In addition, children will be monitored for the occurrence of symptomatic recurrent thrombosis and bleedings. All suspected clinical study outcomes and baseline and repeat ultrasound imaging tests will be assessed by a Central Independent Adjudication Committee (CIAC). An independent data monitoring committee (DMC) will monitor the children's safety and give recommendations to the steering committee.

[...]

Table 2: Flow chart: pharmacokinetics and pharmacodynamics

PK and PD ^a	Visit 1	Visit 2						Visit 3						Visit 4
Rivaroxaban treatment days	Screen day -10 to day 1	Treatment day 1			Treatment day 2			Treatment day 3			Treatment day 4 to 7			Day 8
Rivaroxaban administration		1 st dose	2 nd dose	3 rd dose	1 st dose	2 nd dose	3 rd dose	1 st dose	2 nd dose	3 rd dose	1 st dose	2 nd dose	3 rd dose	
PK/PD time points		0.5 to 3 hr post dose	7 to 8hr post dose					0.5 to 3 hr post dose	7 to 8hr post dose					10-16 hr after last dose at day 7
Obtain blood sample for PK ^b		•	•					•	•					
Obtain blood sample for PD ^c			•					•						• ^d

hr = hour(s), PD = pharmacodynamics, PK = pharmacokinetics
^a The approximate total blood volume taken per child for PK/PD is 6.6 mL. Always draw the PD sample as the last sample.
^b Blood volume per PK sample is approximately 0.6 mL; total blood volume for all PK samples is 2.4 mL.
^c Blood volume per PD sample is approximately 1.4 mL; total blood volume for all PD samples is 4.2 mL.
^d If continued treatment with anticoagulants is necessary, administer the anticoagulant after last sample is taken for rivaroxaban.

16.3.2.3 Section 1 Introduction

This section was modified based on Change 3.

Old text:

[...]

In this phase I/II study, children with confirmed symptomatic or asymptomatic arterial or venous thrombosis will be treated for 7 days with the age- and body weight-adjusted rivaroxaban ~~twice~~ daily dosing regimen to achieve a similar exposure as that observed in adults treated for VTE with 20 mg rivaroxaban once daily.

[...]

New text:

[...]

In this phase I/II study, children with confirmed symptomatic or asymptomatic arterial or venous thrombosis will be treated for 7 days with the age- and body weight-adjusted rivaroxaban three times daily dosing regimen to achieve a similar exposure as that observed in adults treated for VTE with 20 mg rivaroxaban once daily.

[...]

16.3.2.4 Section 3.1 Study description

This section was modified based on Change 3.

Old text:

[...]

Neonates and infants aged less than 6 months who pass the screen of in- and exclusion criteria, who have been treated for at least five days with heparin and /or VKA for confirmed symptomatic or asymptomatic arterial or venous thrombosis are eligible for the study. Study treatment consists of a 7-day treatment with an age- and body weight-adjusted ~~twice~~ daily oral rivaroxaban dosing to achieve a similar exposure as that observed in adults treated for venous thromboembolism (VTE) with 20 mg rivaroxaban once daily. Rivaroxaban will be provided as granules for preparation of an oral suspension (1 mg/mL after re-suspension) using a ~~b.i.d.~~ regimen with ~~12~~-hour intervals.

[...]

New text:

[...]

Neonates and infants aged less than 6 months who pass the screen of in- and exclusion criteria, who have been treated for at least five days with heparin and /or VKA for confirmed symptomatic or asymptomatic arterial or venous thrombosis are eligible for the study. Study treatment consists of a 7-day treatment with an age- and body weight-adjusted three times daily oral rivaroxaban dosing to achieve a similar exposure as that observed in adults treated for venous thromboembolism (VTE) with 20 mg rivaroxaban once daily. Rivaroxaban will be provided as granules for preparation of an oral suspension (1 mg/mL after re-suspension) using a t.i.d. regimen with 8-hour intervals.

[...]

16.3.2.5 Section 5.1.1 Rivaroxaban regimen

This section was modified based on Change 3.

Old text:

[...]

Age- and body weight-adjusted rivaroxaban will be administered ~~twice~~ daily (approximately ~~12~~ hours apart) as oral suspension. ~~Rivaroxaban will be taken in the morning and evening immediately before or (early) during feeding.~~

~~If a rivaroxaban dose was missed, the child should take rivaroxaban immediately to ensure intake of the total daily dose per day. In this case, two oral suspension doses may be taken at once. Thereafter, the child should continue with the regular b.i.d. rivaroxaban administrations.~~

[...]

Table 3: Rivaroxaban dosing schedule

Body weight [kg]		Oral suspension dose (b.i.d.)	Total daily dose
Min	Max	[mg]	[mg]
2.6	<3	0.5	1.0
3	<4	0.6	1.2
4	<5	0.9	1.8
5	<6	1.2	2.4
6	<7	1.6	3.2
7	<8	1.9	3.8
8	<9	2.5	5.0
9	<10	2.7	5.4
10	<12	2.9	5.8
12	<20	3.2	6.4

[...]

New text:

[...]

Age- and body weight-adjusted rivaroxaban will be administered three times daily approximately 8 hours apart as oral suspension. The oral suspension will be administered immediately before or (early) during feeding.

Originally, the study started with a b.i.d. regimen. Rivaroxaban was well tolerated in the 5 children treated according to the b.i.d. regimen and there were no bleeding events. Furthermore, no symptomatic recurrent venous thromboembolic complications occurred.

Repeat imaging of the thrombosis in two children with a persistent thrombosis at the start of rivaroxaban treatment showed normalization and substantial regression of the thrombosis, respectively, after the 7-day treatment with rivaroxaban.

However, PK results of the first 5 children enrolled with the b.i.d. regimen indicate lower rivaroxaban exposure ($AUC_{ss,24h}$) and C_{trough} concentrations than initially expected by the PK model. Based on these observations, the Data Monitoring Committee recommended to change the dosing regimen from a b.i.d. (approx. 12-hour intervals) to a t.i.d. (approx. 8-hour intervals) schedule applying the same individual doses previously administered twice daily. This recommendation was endorsed by the steering committee.

Following implementation of Amendment 5, children will be dosed according to the t.i.d. schedule (according to Table 3). The 50% increase of the total daily dose will increase the exposure, and the shortening of the dosing interval from 12 to 8 hours (t.i.d. schedule) aims to increase the C_{trough} concentrations.

If a rivaroxaban individual dose was missed, the t.i.d. administration schedule with approx. 8-hour intervals should be resumed without compensating for the missed dose.

[...]

Table 3: Rivaroxaban dosing schedule

Body weight [kg]		Oral suspension dose (t.i.d.)	Total daily dose
Min	Max	[mg]	[mg]
2.6	<3	0.5	1.5
3	<4	0.6	1.8
4	<5	0.9	2.7
5	<6	1.2	3.6
6	<7	1.6	4.8
7	<8	1.9	5.7
8	<9	2.5	7.5
9	<10	2.7	8.1
10	<12	2.9	8.7

* to be administered every 8 hours

[...]

16.3.2.6 Section 6.3 Visit 2 – Treatment visit at Day 1

This section was modified based on Change 3.

Old text:

[...]

- At 0.5-~~1.5~~ hr after rivaroxaban, collect only a PK blood sample.
- At ~~2-0~~4 hr after rivaroxaban intake, collect a PK blood sample followed by the PD sample.
- Document the exact time of each blood sampling for PK/PD.
- Obtain ultrasound and prepare an adjudication package to be sent to the adjudication office.

[...]

New text:

[...]

- At 0.5-3 hr after rivaroxaban, collect only a PK blood sample.
- At 7-8 hr after rivaroxaban intake, collect a PK blood sample followed by the PD sample.
- Document the exact time of each blood sampling for PK/PD.
- Obtain ultrasound and prepare an adjudication package to be sent to the adjudication office. In case other diagnostic tests were performed to visualize the clot, these should be sent as well.

[...]

16.3.2.7 Section 6.4 Visit 3 – Treatment visit at Day 3

This section was modified based on Change 3.

Old text:

[...]

- At ~~2-8~~ hr after rivaroxaban, collect a ~~post-dose~~ PK blood sample followed by the PD blood sample.
- Document the exact time of blood sampling for PK/PD.
- Check changes in concomitant medications.
- ~~Inform that on the day before visit 4, the evening dose of rivaroxaban should be taken as late as possible.~~

[...]

New text:

[...]

- At 0.5-3 hr after rivaroxaban, collect a PK blood sample followed by the PD blood sample.
- At 7-8 hr after rivaroxaban intake, collect only a PK blood sample.
- Check changes in concomitant medications.

[...]

16.3.2.8 Section 6.5 Visit 4 – Day 8

This section was modified based on Change 3.

Old text:

[...]

- At 10-16 hr after last rivaroxaban intake, ~~collect the PK blood sample followed by the PD blood sample~~, collect ALT, total and direct bilirubin sample.
- Document the exact time of blood sampling for ~~PK/PD~~.
- Repeat ultrasound and prepare an adjudication package to be sent to the adjudication office. The repeat ultrasound can be performed on day 8 ± 1 .

[...]

New text:

[...]

- At 10-16 hr after last rivaroxaban intake, collect ALT, total and direct bilirubin sample, followed by the PD blood sample. If continued treatment with anticoagulants is necessary, administer the anticoagulant after this sample is taken.
- Document the exact time of blood sampling for PD.
- Repeat ultrasound and prepare an adjudication package to be sent to the adjudication office. The repeat ultrasound can be performed on day 8 ± 1. In case other diagnostic tests were performed to visualize the clot, these should be sent as well.

[...]

16.3.2.9 Section 6.12 PK/PD assessment

This section was modified based on Change 3.

Old text:

[...]

- two post-dose PK samples at visit 2
- one post-dose PD sample at visit 2
- one post-dose ~~PK/PD~~ sample at visit 3
- one post-dose ~~PK/PD~~ sample at visit 4

[...]

New text:

[...]

- two post-dose PK samples at visit 2
- one post-dose PD sample at visit 2
- two post-dose PK sample at visit 3
- one post-dose PD sample at visit 3
- one post-dose PD sample at visit 4

[...]

[figure not shown]
17. Appendices

17.1.1 Bioanalytics and pharmacokinetics

Rivaroxaban concentrations in plasma will be measured by a validated high-performance liquid chromatography assay with tandem mass spectrometric detection. Quality control and calibration samples will be analyzed concurrently with study samples. The results of quality check samples will be reported together with concentrations in unknown samples in the clinical study report. Concentrations are calculated from the chromatographic raw data in accordance with current Bayer guidelines. Only values above the lower limit of quantification are used to determine pharmacokinetic parameters.

Rivaroxaban (BAY 59-7939, JNJ-39039039) is being co-developed under a collaboration and license agreement between Bayer HealthCare AG and Ortho McNeil Pharmaceuticals, Inc. dated 01 Oct 2005. As determined by the parties, both Bayer HealthCare AG and Janssen Pharmaceuticals Inc. (successor in interest to Ortho McNeil Pharmaceuticals, Inc.) may use affiliated corporate entities to conduct this clinical study. With regard to Janssen Pharmaceuticals Inc., such affiliates may include Janssen Research & Development, LLC (formerly Johnson & Johnson Pharmaceutical Research & Development LLC), Janssen Scientific Affairs, LLC, and Janssen-Cilag International N.V. The term “sponsor” or “designee” is used to represent these various legal entities that have been identified to perform various clinical study services; the actual sponsor or designee is identified on the Contact Information page that accompanies this protocol.

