5.1 Method of treatment allocation

5.1.1 Rivaroxaban regimen - amended

Age- and body weight-adjusted rivaroxaban will be administered three times daily approximately 8 hours apart as oral suspension. The oral suspension will be administered immediately before or (early) during feeding.³¹

Originally, the study started with a b.i.d. regimen. Rivaroxaban was well tolerated in the 5 children treated according to the b.i.d. regimen and there were no bleeding events. Furthermore, no symptomatic recurrent venous thromboembolic complications occurred. Repeat imaging of the thrombosis in two children with a persistent thrombosis at the start of

²⁷ Exclusion criterion 9 was modified via Amendment 1 (see Section 16.1.2.3)

²⁸ Exclusion criterion 10 was modified via Amendment 1 (see Section 16.1.2.3)

²⁹ Exclusion criterion 12 was modified via Amendment 4 (see Section 16.2.2.9)

³⁰ This section was modified via Amendment 4 (see Section 16.2.2.10)

³¹ Throughout the complete section t.i.d. dosing was introduced via Amendment 5 (see Section 16.3.2.5)

rivaroxaban treatment showed normalization and substantial regression of the thrombosis, respectively, after the 7-day treatment with rivaroxaban.

However, PK results of the first 5 children enrolled with the b.i.d. regimen indicate lower rivaroxaban exposure ($AUC_{ss,24h}$) and C_{trough} concentrations than initially expected by the PK model. Based on these observations, the Data Monitoring Committee recommended to change the dosing regimen from a b.i.d. (approx. 12-hour intervals) to a t.i.d. (approx. 8-hour intervals) schedule applying the same individual doses previously administered twice daily. This recommendation was endorsed by the steering committee.

Following implementation of Amendment 5, children will be dosed according to the t.i.d. schedule (according to [Table 3](#)). The 50% increase of the total daily dose will increase the exposure, and the shortening of the dosing interval from 12 to 8 hours (t.i.d. schedule) aims to increase the C_{trough} concentrations.

If a rivaroxaban individual dose was missed, the t.i.d. administration schedule with approx. 8-hour intervals should be resumed without compensating for the missed dose.

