6.4 Visit 3 – Treatment visit at Day 3 - amended

The following assessments and procedures have to be performed on visit 3:⁴²

- Check for potential study outcomes. If a suspected study outcome occurred, an adjudication package needs to be compiled and sent to the adjudication office.
- Check for adverse events.

³⁹ This section was modified via Amendment 1 and 5 (see Section 16.1.2.7 and 16.3.2.6)

⁴⁰ Bullet was modified via Amendment 4 (see Section 16.2.2.16)

⁴¹ Bullet was modified via Amendment 1 (see Section 16.1.2.7)

⁴² This section was modified via Amendment 4 (see Section 16.2.2.17)

- Collect body weight and if needed adjust the dosage of rivaroxaban.
- Administer the next dose of rivaroxaban according to the oral suspension handling guidelines. ⁴³
- Document the exact time of rivaroxaban intake and the type (e.g. breast milk, formula, porridge, or pureed food) and estimated volume of food rivaroxaban was administered with.
- In case rivaroxaban is administered together with porridge or pureed food, encourage the child to drink a typical serving of liquid thereafter (e.g., breast milk, formula, water, juice) and document the type of liquid and the estimated volume.
- At 0.5-3 hr after rivaroxaban, collect a PK blood sample followed by the PD blood sample.
- At 7-8 hr after rivaroxaban intake, collect only a PK blood sample.
- Document the exact time of blood sampling for PK/PD.
- Check changes in concomitant medications.
- Instruct to document in the study booklet
 - the exact time of the last dose of rivaroxaban on the day prior to visit 4,
 - the type (e.g. breast milk, formula, porridge, or pureed food) and estimated volume of fluid (e.g. breast milk and formula) or food (e.g. porridge or pureed food) rivaroxaban was administered with, ⁴⁴
 - In case rivaroxaban is administered together with porridge or pureed food, parents should document the type and estimated volume of liquid (e.g., breast milk, formula, water, juice) that the child took thereafter.
- Update eCRF.

⁴³ Bullet was modified via Amendment 4 (see Section 16.2.2.17)

⁴⁴ Bullet was modified via Amendment 1 (see Section 16.1.2.8)

If a child discontinues rivaroxaban permanently before visit 3, visit 3 will still need to take place:

- Check for potential study outcomes. If a suspected study outcome occurred, an adjudication package needs to be compiled and sent to the adjudication office.
- Check for adverse events. If an adverse event occurred, update the eCRF.

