7.6 PK/PD analysis

PK/PD modeling, using population approaches will be used to describe the pharmacokinetics of rivaroxaban, and to relate anticoagulant parameters of rivaroxaban with plasma concentrations.

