### 6.4 PK/PD analysis

#### Pharmacokinetic data

The concentration-times courses of rivaroxaban will be tabulated for each sampling interval. The following statistics will be calculated for each of the sampling intervals: arithmetic mean, standard deviation and coefficient of variation (CV), geometric mean, geometric standard deviation (re-transformed standard deviation of the logarithms) and CV, minimum, median, maximum value and the number of measurements. Means for any interval will only be calculated if at least 2/3 of the individual data were measured and were above the lower limit of quantification (LLOQ). For the calculation of the mean value a data point below LLOQ will be substituted by one half of this limit. In tables showing mean values, where values below LLOQ are included in the calculation of mean values, these means will be marked.

Individual and geometric mean concentration vs time curves of rivaroxaban (using the actual sampling times for individual plots and the planned sampling intervals for mean plots) will be plotted using both linear and semilogarithmic scale.

If applicable, pharmacokinetic characteristics derived via popPK modeling ( $t_{\max}$  excluded) will be summarized by the statistics mentioned above.  $t_{\max}$  will be described utilizing minimum, maximum and median as well as frequency counts.

Comparison with reference data will be graphically sketched.

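### Exclusion is the only written rule for concentrations below the LLOQ in the PK parameters; if any occur, it biases trough upward and exposure less so

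*Protocol*

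**What the plan says.** Protocol 17.1.1 (Bioanalytics and pharmacokinetics) is current text: "Only values above the lower limit of quantification are used to determine pharmacokinetic parameters".

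Protocol 7.6 names the source of the parameters: "PK/PD modeling, using population approaches will be used to describe the pharmacokinetics of rivaroxaban". SAP 6.4 (Pharmacokinetic data) agrees, planning to summarise, if applicable, "pharmacokinetic characteristics derived via popPK modeling".

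SAP 6.4 has its own rule for the tabulated concentrations in each sampling interval: "For the calculation of the mean value a data point below LLOQ will be substituted by one half of this limit". Two safeguards go with it. One is a completeness condition, "Means for any interval will only be calculated if at least 2/3 of the individual data were measured and were above" the LLOQ. The other is a flag: "where values below LLOQ are included in the calculation of mean values, these means will be marked". No rule is given for such values in the model.

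Under t.i.d. dosing, two of the four PK samples per child fall at the end of the 8-hour interval, one on Day 1 and one on Day 3. For the latter, Protocol 6.4 says: "At 7-8 hr after rivaroxaban intake, collect only a PK blood sample". The Day 8 sample at 10-16 h is now for PD only (Protocol Table 2 and 6.5). Under the b.i.d. schedule, still shown in SAP Table 2, it was also a PK sample.

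**The concern.** Values below the LLOQ are not missing at random; they are the lowest concentrations. A model fitted without them, and without being told that they were low, sees only the higher part of the late samples.

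Trough and exposure are what the dosing question turns on. Protocol 5.1.1 reports: "PK results of the first 5 children enrolled with the b.i.d. regimen indicate lower rivaroxaban exposure", and also lower trough concentrations than the PK model had predicted. That led to the t.i.d. schedule. The Amendment 5 rationale (16.3.1.3) wants troughs to match the adult reference range so that adult safety and efficacy can be extrapolated. A rule that removes the lowest troughs leans towards finding that this has been achieved.

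**Working it through.** **1. Which rule covers which output**

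| Output | Source | Rule for values below LLOQ |
|---|---|---|
| Interval concentration means | SAP 6.4 | LLOQ/2, 2/3 condition, marked |
| PK parameters from the population model | Protocol 7.6, SAP 6.4 | Exclusion (Protocol 17.1.1); SAP silent |

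With 8 children, the 2/3 condition tolerates two values below the LLOQ (6/8 = 0.75) but not three (5/8 = 0.625). It protects the tabulated means, not the model.

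**2. The plan's own PK figure**

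Protocol 7.8 gives a 90% interval for the geometric mean AUC of 62% to 161% of the estimate, with n = 8 and geometric CV 80%.
- σ = √ln(1 + 0.80²) = 0.703; t(0.95; 7 df) = 1.895.
- 1.895 × 0.703/√8 = 0.471; exp(±0.471) gives 62.4% to 160.2%.

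This reproduces the figure (161% is 1/0.62). At CV 138% the formula gives 50.1% to 199.7%, against the stated 50% to 200%. Neither figure allows for values below the LLOQ.

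**3. Direction of the bias**

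Assume log-normal troughs with a fraction p below the LLOQ, and z = Φ⁻¹(p). Dropping them multiplies the raw geometric mean by exp[σφ(z)/(1 − p)]. For CV 80% and p = 0.25: 0.318/0.75 = 0.424; 0.424 × 0.703 = 0.298; exp(0.298) = 1.35. With LLOQ/2 the factor is 0.93. At CV 40% and p = 0.25 the two factors are 1.18 and 0.89. Over p from 1/8 to 1/2 and CV from 40% to 138%, dropping gives 1.09 to 2.28 and LLOQ/2 gives 0.82 to 1.07.

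This fixes the sign only. The plan computes no raw trough mean after deletion, so these factors do not measure the bias in any planned output.

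**4. Size in a population fit**

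All parameters are assumed:
- one-compartment model at steady state, 8-hour interval, 8 children;
- one sample at 0.5-3 h and one at 7-8 h per child;
- SD of log clearance 0.6, that is geometric CV √(exp(0.36) − 1) = 66%;
- residual SD 0.3 on the log scale;
- volume, absorption rate and residual SD held at their true values;
- 60 replicates, with both methods fitted to the same simulated data.

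Ratio of estimate to truth:

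| Troughs below LLOQ | Trough, dropped | Trough, censored | AUC, dropped | AUC, censored |
|---|---|---|---|---|
| 12.5% | 1.03 | 1.02 | 1.01 | 1.01 |
| 25% | 1.17 | 1.00 | 1.07 | 1.00 |
| 50% | 1.44 | 1.11 | 1.19 | 1.05 |

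Monte Carlo error is about 2-3% for AUC. Trough moves about twice as much as AUC on the log scale (ln 1.17/ln 1.07 = 2.3; ln 1.44/ln 1.19 = 2.1), so its error is roughly twice as large. At 12.5% the methods cannot be told apart. At 25% they differ clearly for trough and modestly for AUC. AUC is less affected because it also rests on the 0.5-3 h samples.

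**The case against.** **No value below the LLOQ is documented.** Neither document gives the limit or reports a value under it. Low exposure in the first five children was low against a model prediction, which does not mean unquantifiable. The t.i.d. schedule aims to raise troughs and no longer has a PK sample at 10-16 h, the time most prone to such values. Of the two 7-8 h samples, the Day 1 sample is not a steady-state trough. All of this stands, and it makes the point conditional. The late PK samples do exist for the b.i.d. children, however. Whether their data are pooled into the same model is not stated.

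**The appendix sentence may not govern the model.** It is a general statement in a bioanalytical appendix. But it speaks of PK parameters, the population model is the stated source of those, and nothing else covers them.

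**The decision is informal.** The aim is to characterise the profile, there is no numerical criterion, and comparison with reference data is graphical. With about eight children and individual curves plotted, low values are unlikely to go unseen. This limits the consequence but does not justify the rule.

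**Inferences to resist.** A reader might take the raw-mean factors, such as 1.35, as the bias in the reported parameters; the population fit gives about half that excess for trough (1.17) and far less for AUC (1.07). A reader might also say that the protocol and SAP rules contradict each other; they cover different outputs. Or that the rule undermines the move to t.i.d.; applied to the b.i.d. data, it would have worked against finding low levels.

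**Conclusion.** The plan sets a rule that, when it has any effect, biases the estimated trough upward and exposure usually upward but less. It offers no correction for model-derived parameters. With no values below the LLOQ the effect is nil.

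Under the assumed model, exclusion adds almost nothing with one trough in eight below the LLOQ. With one in four it adds about 17% to typical trough and 7% to AUC. The AUC shift is small beside the plan's own 62% to 161% interval, but that interval is random error, whereas this shift has a known direction.

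A reader might conclude that trough and exposure will be overstated. The documents do not support that, because they do not show that any value is below the limit. Confidence in the direction is high and in the size low. Severity is minor to moderate. What matters is the judgement whether t.i.d. troughs reach the adult range.

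**What to change.** Replace the sentence in Protocol 17.1.1 and add to SAP 6.4:
- Samples below the LLOQ stay in the population PK dataset as left-censored observations, fitted with a censored likelihood (M3).
- A fit excluding them is a sensitivity run. State in advance what will be reported if the censored fit does not converge.
- Report the LLOQ and the number of values below it by sampling window and regimen (b.i.d. or t.i.d.).

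The LLOQ/2 rule for interval means can stay, with the windows updated. The SAP is based on protocol version 2.0 and still lists b.i.d. sampling times, so it needs revision in any case.

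The cost is a few sentences and a standard model option, with no extra blood. The drawbacks are longer run time and possible instability with about eight children. The censored fit is also not exact when half the troughs are below the LLOQ (trough 1.11, AUC 1.05 above), which is another reason to show both fits.
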